4.7.2 Vital Signs

Vital signs will be measured at each treatment visit including at screening and early termination visits whereas unscheduled visit is optional. Analyses of vital signs will be performed in the following manner:

- Descriptive statistics of vital signs before first study dose and afterwards as well as the changes from baseline by scheduled visit will be generated.
- Vital signs will be graded based on table 2 in appendix C of the protocol:

TABLE 2: GRADING OF VITAL SIGNS

Vital Signs	Mild (Grade 1)	Moderate (Grade 2)	Severe (Grade 3)	Potentially Life Threatening (Grade 4)
Fever (°C) (°F)	38.0 – 38.4 100.4 – 101.1	38.5 – 38.9 101.2 – 102.0	39.0 – 40 102.1 – 104	> 40 > 104
Tachycardia - BPM	101 – 115	116 – 130	> 130	ER visit or hospitalization for arrhythmia
Bradycardia - BPM	50 – 54	45 – 49	< 45	ER visit or hospitalization for arrhythmia
Hypertension (systolic) - mm Hg	141 – 150	151 – 155	> 155	ER visit or hospitalization for malignant hypertension
Hypertension (diastolic) - mm Hg	91 – 95	96 – 100	> 100	ER visit or hospitalization for malignant hypertension
Hypotension (systolic) – mm Hg	85 – 89	80 – 84	< 80	ER visit or hospitalization for hypotensive shock
Respiratory Rate – breaths per minute	17 – 20	21 – 25	> 25	Intubation

- The incidence (no. of subjects) of vital signs grading will be summarized in a frequency tables.
- Box-Plots of vital signs before first study dose and afterwards by scheduled visit will be provided by request for specific parameters. .

4.7.3 Laboratory Test Results

Analyses of safety laboratory data will be performed in the following manner:

- Descriptive statistics of quantitative tests results and changes from baseline by scheduled visit.
- Quantitative laboratory measurements will be categorized with reference to the normal ranges as Low, Normal or High. Incidence tables of laboratory results categories will be presented by visit.
- Incidence tables of CS lab values defined by the PI as well as the individual subject listing will also be provided.
- Box-Plots of laboratory measurements from first study dose and afterwards by scheduled visit will be provided by request for specific parameters.

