10.9.2 Vital Signs

Vital signs will be measured at each treatment visit including at unscheduled or early termination visits. Analyses of vital signs were performed in the following manner:

- Box-Plots of vital signs before first study dose and afterwards by scheduled visit will be generated.
- Descriptive statistics of vital signs before first study dose and afterwards as well as the changes from baseline by scheduled visit will be generated.
- The incidence (no. of subjects) of potentially clinically significant (PCS) abnormal values will be summarized in a frequency table and will be listed.

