10.9.3 Laboratory Evaluations

Analyses of safety laboratory data will be performed in the following manner:

- Box-Plots of laboratory measurements first study dose and afterwards by scheduled visit will be provided.
- Descriptive statistics of quantitative tests results and changes from baseline by scheduled visit.
- Quantitative laboratory measurements will be categorized with reference to the normal ranges as Low, Normal or High. Shift analysis of the categorical change from baseline to each scheduled visit and to the last observed assessment will also be presented.
- Incidence tables of PCS lab values as well as the individual subject listing will also be provided.

	Protocol No.: SciB018
	Version and Date: Version 2.0, September 9, 2015 Amendment 1

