7. APPENDIX III: FIGURES

Figure number	Title
Figure 1	SPR by month, mITT
Figure 2	SPR by month, FT (for first IA mITT who completed Month 7)
Figure 2.1	Percentage of non-responder, responder and high-responder to Sci-B-Vac™ by Month, mITT (second interim analysis)
Figure 3	Geometric Mean of anti-HBs Antibody titers by month, mITT
Figure 4	Geometric Mean of anti-HBs Antibody titers by month, FT (for first IA mITT who completed Month 7)
Figure 5	Geometric Mean of anti-HBs Antibody titers by month and Gender
Figure 6	Geometric Mean of anti-HBs Antibody titers by month and Age
Figure 7	Geometric Mean of anti-HBs Antibody titers by month and Smoking status
Figure 8	Geometric Mean of anti-HBs Antibody titers by month and BMI

* Box plots for laboratory results and vital signs will be generated for specific parameters, based on the results and the sponsor's request.

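### The SAP replaces the protocol's laboratory shift analysis with by-visit counts not paired with baseline, and makes box plots selective, with no recorded reason

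*SAP*

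**What the plan says.** **Protocol v2.0.** Section 10.9.3 classes quantitative laboratory results as Low, Normal or High against the normal range and then states: "Shift analysis of the categorical change from baseline to each scheduled visit and to the last observed assessment will also be presented". The same section says of the plots: "Box-Plots of laboratory measurements first study dose and afterwards by scheduled visit will be provided". Section 10.9.2 says the same for vital signs: "Box-Plots of vital signs before first study dose and afterwards by scheduled visit will be generated". None of these carries a condition. The wording is identical in protocol v1.0, so it survived an amendment that rewrote other parts of section 10.

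**SAP.** Section 4.7.3 repeats the Low/Normal/High classification, but the sentence that follows is now: "Incidence tables of laboratory results categories will be presented by visit". The laboratory plots become: "Box-Plots of laboratory measurements from first study dose and afterwards by scheduled visit will be provided by request for specific parameters". Section 4.7.2 makes the same change for vital signs. The footnote to Appendix III gives the selection rule: "Box plots for laboratory results and vital signs will be generated for specific parameters, based on the results and the sponsor's request". The table list in Appendix I contains no shift table.

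Section 4.7.3 also retains: "Descriptive statistics of quantitative tests results and changes from baseline by scheduled visit". It keeps incidence tables of values that the investigator judges clinically significant, with a subject listing.

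**The concern.** The trial has one arm. With no concurrent control, a subject's own pre-vaccination value is the natural reference for reading a later out-of-range result, and monitoring safety is a stated secondary objective. A shift table crosses each subject's baseline class with the later class. A by-visit count gives only the two margins of that cross-table. Equal counts at baseline and at a later visit fit both complete stability and complete turnover.

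The box plots raise a separate, smaller issue. A figure that the protocol promised for the measurements generally is now produced only for parameters chosen once the results are known, partly at the sponsor's request. A reader of the report could not tell why some parameters were plotted and others were not.

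**Working it through.** The plan states no figure on this point, so there is nothing to reproduce. The check is a comparison of the texts, followed by a bound on what the planned table can show.

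**1. Side by side**

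| Item | Protocol v2.0, 10.9.2–10.9.3 | SAP |
|---|---|---|
| Low/Normal/High classes | Yes | Yes (4.7.3) |
| Class crossed with baseline, each visit | Yes | No; counts by visit (4.7.3) |
| Class crossed with baseline, last assessment | Yes | No replacement in 4.7.3 or Appendix I |
| Laboratory box plots | Unconditional | On request, selected parameters (4.7.3, Appendix III) |
| Vital-sign box plots | Unconditional | On request, selected parameters (4.7.2, Appendix III) |
| Numerical change from baseline | Yes | Yes (4.7.3; Tables 14.3.6, 14.3.8, 14.3.10; vital signs 14.3.13) |

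Appendix I also lists out-of-range tables (14.3.4-2, -4 and -6). Neither their titles nor the text of 4.7.3 pairs them with baseline.

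The SAP version history records other changes, including the deletion of a GMC ratio, but does not mention the shift analysis. It tracks changes between SAP versions only, so its silence does not show when the analysis was left out. It shows only that no reason is recorded there.

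**2. What by-visit counts can identify**

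Let n subjects be measured at both times, with b High at baseline and v High at the later visit. The number newly High must lie between

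- lower bound = max(0, v − b)
- upper bound = min(v, n − b)

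n = 92 is the enrolment ceiling in SAP 2.4, n = 84 is that in protocol 5.1, and n = 70 is the sample size in the justification in both documents. The counts b and v are assumptions, because the documents give none.

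| n | b | v | Newly High | As % of the n − b not High at baseline |
|---|---|---|---|---|
| 92 | 4 | 4 | max(0, 0) = 0 to min(4, 88) = 4 | 0 to 4/88 = 4.5% |
| 92 | 10 | 10 | 0 to 10 | 0 to 10/82 = 12.2% |
| 92 | 5 | 10 | 5 to 10 | 5/87 = 5.7% to 10/87 = 11.5% |
| 84 | 10 | 10 | 0 to 10 | 0 to 10/74 = 13.5% |
| 70 | 10 | 10 | 0 to 10 | 0 to 10/60 = 16.7% |

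A shift table would give the exact number in every row.

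**3. Whether the retained summaries fill the gap**

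The change-from-baseline tables are paired but do not use the normal range. If four subjects rise by d and leave the range while four others fall by d and return to it, their contribution to the mean change is 4d − 4d = 0. The standard deviation and extremes would show spread, but not who crossed a limit.

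The clinically significant value tables use the normal range only through the investigator's judgement. Under protocol 9.1 a laboratory abnormality not judged clinically significant is not an adverse event, so such values need not appear in the adverse event tables either.

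**The case against.** The strongest reply is that little is lost. Within-subject change is pre-specified for haematology, chemistry, urinalysis and vital signs. SAP 3.2 lists all measured variables individually. Clinically significant abnormalities are reported as adverse events (protocol 6.4.6), a new or worsened condition counts as one (protocol 9.1), and SAP 4.7.1 analyses only events starting on or after the day of first dose. Subjects with clinically significant laboratory abnormalities at screening are not eligible. So the abnormalities that matter most are already separated into new and old. All of this stands, and it limits the point to a summary-level display.

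Three stronger readings are tempting, and the documents do not support them.

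- **A reader might infer that the plan as a whole cannot tell new abnormalities from old ones.** It can, through the subject listings and the adverse event rules. Only the planned category tables cannot.
- **A reader might infer that the safety reporting is driven by the results.** The footnote covers box plots only. The adverse event, out-of-range, clinically significant, by-visit and change-from-baseline tables are fixed in advance.
- **A reader might size the problem by the out-of-range values expected by chance.** For 22 chemistry and haematology tests and an assumed 5% rate, this is 22 × 0.05 × 84 = 92.4 per visit, or 22 × 0.05 × 92 = 101.2. That total is the same with or without a shift table, so it does not measure the loss.

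Two limits of the documents also count. The SAP enrols up to 92 subjects against 84 in protocol v2.0, and it refers to changes in the protocol, so a later protocol may exist and may have altered section 10.9.3. SAP Appendix II (listings) was not available for this check. Protocol 10.10 also allows deviations to be explained in the study report, although that would come after the results are known.

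**Conclusion.** The point holds in limited form. On the documents supplied, the SAP omits a shift analysis that the protocol plans and puts unpaired counts in its place. The baseline-to-last-assessment comparison of classes disappears altogether. What is lost is the one planned laboratory summary that was paired with baseline, referred to the normal range and did not depend on open-label investigator judgement. The loss falls mainly on values not judged clinically significant.

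The box plots have moved from unconditional to selected after the results are seen. That is a lesser matter of presentation, because the numerical summaries behind them are planned without selection.

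Severity is minor: this is a secondary safety display, with no effect on the primary endpoint. The size cannot be stated from the documents. The ranges above rest on assumed counts and on the same subjects being measured at both times. The conclusion also assumes that no later protocol version removed the analysis.

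**What to change.** - **SAP 4.7.3 and Appendix I:** reinstate the Low/Normal/High shift tables from baseline to each scheduled post-baseline laboratory visit and to the last observed value.
- **Baseline:** state which pre-dose sample is used. Laboratory tests are done both at screening and at Visit 2 before dosing (protocol 6.4.6), and neither laboratory analysis section says which is baseline. The choice is for the sponsor, and it determines which visits count as post-baseline.
- **SAP 4.7.2, 4.7.3 and Appendix III:** name the box-plot parameters in advance, or produce the plots for all of them, and delete the rule that selects on results and sponsor request.
- **If the omission is deliberate:** cite the protocol version that removed the shift analysis, or record the deviation and its reason as protocol 10.10 requires.

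The cost is a few programmed tables and figures. The data are already collected, and no visit or sample is added.

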4.7.4 Other Safety Assessments

Summary statistics of other safety evaluations including assessment of ECG, local safety evaluations and pain evaluations (i.e. local reaction grading) will be tabulated and listed.

5. APPENDIX I: TABLES TO BE INCLUDED IN THE STATISTICAL REPORT

Table number	Table Title
14.1	Demographic and Baseline Data
14.1-1.1	Disposition of subjects
14.1-1.2	Primary reason for early discontinuation
14.1-2.1	Analysis population
14.1-3.1	Demographic and Baseline data, ITT
14.1-4	Medical History, ITT
14.1-5	Baseline Physical Examination, ITT
14.1-6	Any Concomitant Medication, ITT
14.1-7	Any Concomitant Non-drug Medication, ITT
14.1.2	Exposure to Sci-B-Vac injection
14.1.2.1	Sci-B-Vac injection, ITT
14.2	Efficacy Analysis
14.2-1	Seroprotection rate (SPR) by Month, mITT
14.2-2	Seroprotection rate (SPR) by Month, FT (for first IA mITT who completed month 7 will be presented)
14.2-3	Secondary Endpoint Analysis: Percentage of Subjects with Anti-HBs \geq 100 mIU/ml by Month, mITT
14.2-4	Secondary Endpoint Analysis: Percentage of Subjects with Anti-HBs \geq 100 mIU/ml) by Month, FT (for first IA mITT who completed month 7 will be presented)
14.2-5	Geometric means of anti-HBs antibody titers by month, mITT
14.2-6	Geometric means of anti-HBs antibody titers by month, FT (for first IA mITT who completed month 7 will be presented)
14.2-7	Frequency of gender by responders (SPR) (at month 4 for first IA)
14.2-8	Frequency of age categories by responders (SPR) (at month 4 for first IA)
14.2-9	Frequency of Responders (SPR) by Smoking status and month (month 4 for IA)
14.2-10	Frequency of Responders (SPR) by BMI categories and month (at month 4 for first IA)
14.2-11	Geometric means of anti-HBs antibody titers by month and Gender
14.2-12	Geometric means of anti-HBs antibody titers by month and age categories
14.2-13	Geometric means of anti-HBs antibody titers by month and Smoking status
14.2-14	Geometric means of anti-HBsAg antibody titers by month and BMI categories
14.2-15	Serologic Markers for Hepatitis B Infection, ITT
14.3	Safety Data
14.3.1	Adverse Events
14.3.1	Summary Incidence of TEAE (Treatment Emergent Adverse Events), ITT
14.3.1-1	Summary of Adverse Events by SOC and PT, ITT

Table number	Table Title
14.3.1-2	Summary of Adverse Events by SOC and PT and Severity, ITT
14.3.1-3	Summary of Adverse Events by SOC and PT and Relation to study drug, ITT
14.3.1-4	Summary of Serious Adverse Events by SOC and PT, ITT
14.3.2	Listing of SAEs (if applicable)
14.3.2-1	Listing of Serious Adverse Events
14.3.4	Abnormal Laboratory Results
14.3.4-1	Incidence of Hematology Abnormal Clinically Significant Results
14.3.4-2	Out of Range Hematology Results
14.3.4-3	Incidence of Chemistry Abnormal Clinically Significant Results
14.3.4-4	Out of Range Chemistry Results
14.3.4-5	Incidence of Urinary Abnormal Clinically Significant Result
14.3.4-6	Out of Range Urinary Result
14.3.4-7	Pregnancy test (Females)
14.3.5	Other Safety Assessment
14.3.5	Summary statistics of Hematology results by Visit
14.3.6	Summary statistics of Hematology Changes from Baseline by Visit
14.3.7	Summary statistics of Chemistry results by Visit
14.3.8	Summary statistics of Chemistry Changes from Baseline by Visit
14.3.9	Summary statistics of Urinalysis results by Visit
14.3.10	Summary statistics of Urinalysis Changes from Baseline by Visit
14.3.11	Summary of Vital Signs by Visit
14.3.12	Frequency of Vital Signs Grading by Visit
14.3.13	Summary of Vital Signs Changes from Baseline (pre-vaccination) by Visit
14.3.14	ECG Assessment
14.3.15	Local Reaction
14.3.16	Any Change in Subject's Health and in concomitant medications since last visit

7. APPENDIX III: FIGURES

Figure number	Title
Figure 1	SPR by month, mITT
Figure 2	SPR by month, FT (for first IA mITT who completed Month 7)
Figure 2.1	Percentage of non-responder, responder and high-responder to Sci-B-Vac™ by Month, mITT (second interim analysis)
Figure 3	Geometric Mean of anti-HBs Antibody titers by month, mITT
Figure 4	Geometric Mean of anti-HBs Antibody titers by month, FT (for first IA mITT who completed Month 7)
Figure 5	Geometric Mean of anti-HBs Antibody titers by month and Gender
Figure 6	Geometric Mean of anti-HBs Antibody titers by month and Age
Figure 7	Geometric Mean of anti-HBs Antibody titers by month and Smoking status
Figure 8	Geometric Mean of anti-HBs Antibody titers by month and BMI

* Box plots for laboratory results and vital signs will be generated for specific parameters, based on the results and the sponsor's request.

8. APPENDIX IV: LISTINGS OF SCREENING FAILURES

Listing number	Listing Title
18.1	Demographic and Baseline data
18.2.4-1	Demographic and baseline data
18.2.4-2	Medical History
18.2.4-3	Baseline Physical Examination
18.2.4-6	Baseline Serology Markers for Hepatitis B Infection
18.2.5	Reasons for Screening Failure
18.2.5	Reasons for Screening Failure
Table	Summary of Reasons for Screening Failure
18.2.5	
18.2.8	Listing of individual laboratory and other assessments by subject
18.2.8-2	Hematology Results
18.2.8-4	Chemistry Results
18.2.8-6	Urinalysis Results
18.2.8-7	Pregnancy Blood Test (Females)
18.2.8-8	Vital Signs
18.2.8-9	ECG Assessment
18.2.8-10	Screening Serology

9. VERSION HISTORY:

Version	Date	Section	Changes	Done By
1.0	22/Feb/2016		Original Release	
1.1	23/Jun/2016	abbreviations	Added/deleted abbreviations	[name]/ [name]
		2.3	Study flow chart was revised according to changes in the protocol	
2.0	23/Jul/2016	4.4	Added analyses by gender, age, BMI and smoking, Defining age, BMI and smoking categories	[name]/ [name]
		4.5	Adding figures for SPR, GMC Delete GMC ratio	
		2.7	Update interim analysis report description	
3.0	18/Sep/2016	Appendix I and II	Minor edits to tables and listings names/tables	[name]/ [name]
		4.7.2	Add text to table 2 (vital signs grading)	
4.0	24/May/2017	2.7	Adding second Interim Analysis	[name]
		Appendix I and III	Minor edits to tables names	
		Appendix II	Correct order of listings Add listings 16.2.8-7-2 and 16.2.8-7-3	

